After routine referral to the study team, we will invite potential participants to a screening session to check their eligibility. Inclusion criteria will be: left-hemispheric cortical or subcortical ischemic or haemorrhagic event; subacute phase (0.5–6 months after the cerebrovascular lesion); German as first native language; right-handedness according to the Edinburgh Handedness Inventory;²⁹ diagnosis of PSD, as defined by international classification code F06.32;⁵ diagnosis of aphasia, as confirmed by the Bielefeld Aphasia Screening, with no more than two standard deviations below the average score on the subscale “Auditory Comprehension” to ensure understanding of basic instructions.³⁰ Exclusion criteria will be: other psychopathological or neurological conditions; premorbid history of recurrent depressive disorder; severe uncorrected vision or hearing that may prevent intensive social interaction during therapy or testing; serious non-verbal cognitive deficits, as revealed by the Corsi Block-Tapping Task.³¹

A target sample of 60 individuals will participate in the present phase-IIb trial. This sample size was calculated in an *a-priori* power analysis ($\alpha = 0.05$; $1-\beta = 0.80$; Cohen's $f = 0.390$; numerator degrees of freedom: 1; number of groups: 2; number of covariates: 2; resulting $n = 54$; expected dropout rate = 10%; final $n = 60$).³² Our effect size estimate derives from published phase-IIa RCT data on Beck's Depression Inventory (BDI), as specified below (converted from $\eta^2 = 0.132$).²⁰ Notably, an extended goal of the current phase-IIb trial will be to deliver a more precise effect size estimate for a subsequent phase-III RCT. We assumed a more conservative dropout rate for ILAT than seen in previous work.^{19,23}

^a Study on aspects of feasibility and potential efficacy as an intermediate step to a phase-III RCT.

Quasi-randomisation and blinding

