Eligible candidates will be assigned to one of two treatment arms (each $n = 30$). Our ILAT protocol requires three individuals with aphasia to be present simultaneously in a rehabilitation centre for daily sessions over a 1-month treatment period. During the recruitment phase, occasionally fewer than three eligible candidates per treatment period will stay at the rehabilitation centre. To meet this logistical challenge in our phase-IIb trial—with a focus on treatment feasibility in PSD—candidates will receive ILAT only if enough fellow players are available to form groups of three individuals. Otherwise, candidates will receive the control intervention. The quasi-randomisation procedure will be administered by a person who does not participate in any stage of therapy or testing. A neuropsychologist with expertise in aphasia will perform all diagnostic sessions. This person will be blinded to group assignment and will not have patient contact aside from the testing. Data will be unmasked for final evaluation purposes by the study team who will not attend any of the therapy or testing sessions.

Treatment and procedures

ILAT requires individuals with aphasia to engage in everyday request and planning communication.¹⁸ Groups of three individuals and a therapist are seated around a table and provided with picture cards showing different objects (e.g., bottle) or action scenes (e.g., drinking). Barriers on the table prevent players from seeing each other's cards. Each card has a duplicate that belonged to one of the other players. The goal is to obtain this duplicate from a fellow player by requesting the depicted object (e.g., “Give me the [...]”) or by proposing an action based on the visualised scene (e.g., “Let's [...] together”). The rich turn-taking structure of ILAT serves as a vehicle for intensive use of formulaic expressions: (i) If the duplicate is available, the players compare the depicted objects or scenes; in the case of a match, the addressee hands over the corresponding card to the person who initiated the request or action-planning sequence (e.g., “Here you are”—“Thank you”—“You're welcome”). (ii) If the duplicate is not available, the addressee rejects the request or proposed action (e.g., “I'm sorry”—“No problem”—“Too bad”). (iii) In the event of misunderstandings, the players ask clarifying questions (e.g., “Pardon me?”).

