We will recreate training materials and procedures described previously.²³ The therapist will continuously apply positive reinforcement via encouraging feedback to diminish the likelihood of cognitive-affective distress caused by lack of social stimulation, in line with a common model of depression aetiology.¹ Practical experience with ILAT demonstrates that players often imitate the therapists' behaviour by starting to support one another verbally, thus

multiplying the amount of positive reinforcement exchanged during treatment (e.g., “Well done!”). Self-cueing strategies will be allowed, along with gestures to accompany—but not replace—spoken language. ILAT involves five weekly sessions, each with a duration of one hour, over a total treatment period of one calendar month. We do not set a minimum amount of treatment in our protocol to compensate for missed sessions, since dropout rates for ILAT have been extremely low in prior work.^{19, 23} The treatment will be delivered by a team of speech-language therapists and neuropsychologists who will receive training and continuous supervision before and during the trial.

Standard care will conform to state-of-the-art procedures of rehabilitation centres certified in Germany. Depending on the participants’ diagnoses and needs, standard care will include: antidepressant medication (drug and dosage defined individually by a physician blinded to group randomisation and study purpose; substance classes: selective serotonin reuptake inhibitors, tri- and tetracyclics), occupational therapy (2–3 hours weekly), physiotherapy (2–3 hours weekly), and non-intensive speech-language therapy (2–3 hours weekly with emphasis on phonology, lexicon and syntax, as detailed in a large-scale RCT protocol³³).

Outcomes and testing

Feasibility, our *primary* outcome, will be considered to be met if at least two-thirds of participants in Group I complete all ILAT sessions offered during the 1-month treatment period.

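### Is the primary feasibility rule wrong because it scores one missed session the same as leaving the trial?

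*Combined protocol and SAP*

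**What the plan says.** Under Outcomes and testing, feasibility is the primary outcome and is met if "at least two-thirds of participants in Group I complete all ILAT sessions offered during the 1-month treatment period". Group I is the ILAT arm, planned at 30 people (Quasi-randomisation and blinding). Two depression scales, the BDI and a short Hamilton scale, are co-primary outcomes of potential efficacy.

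Treatment and procedures gives the schedule: "ILAT involves five weekly sessions, each with a duration of one hour, over a total treatment period of one calendar month". The total number of sessions is not stated. The same section says "We do not set a minimum amount of treatment in our protocol to compensate for missed sessions", and gives as its reason "since dropout rates for ILAT have been extremely low in prior work".

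The sample-size paragraph allows for 10% dropout. A footnote to it describes the trial as a "Study on aspects of feasibility and potential efficacy as an intermediate step to a phase-III RCT". The protocol attaches no stop/go decision to the feasibility verdict.

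**The concern.** In its ordinary sense the rule asks for a perfect record from each person. One absence in about 20 daily sessions then weighs as much as leaving on the first day, and the verdict depends on how many records are perfect and not on how much therapy was taken up. A group with nearly full attendance could be called not feasible, and a group that lost a third of its members could be called feasible.

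The reason given for setting no minimum amount of treatment adds to the doubt. It cites low dropout, but under this rule single absences count too, and low dropout does not show that single absences are rare. Since the trial is meant to lead to a phase-III trial, a misleading verdict on the primary outcome would carry forward.

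**Working it through.** **Inputs.** From the protocol: Group I = 30; cut-off two-thirds, so 20 of 30; dropout allowance 10%; five sessions a week for a month. Assumed, because the protocol does not state them: number of sessions S = 20 to 23, attendance rate *a* among those who stay, and clustering of absences within a person (ICC).

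**The plan's own figure.** The only sample-size figure belongs to the BDI analysis, not to the feasibility rule. It reproduces: f = √(0.132/0.868) = 0.390; with two groups and two covariates, N = 54 gives power 0.802 (N = 53 gives 0.795); 54/0.9 = 60. No power or error rate is stated for the feasibility rule.

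**Step 1: the two contrasting patterns.**

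| Pattern | Sessions attended | Perfect records | Verdict |
|---|---|---|---|
| Nobody leaves; 11 miss one session each | 589/600 = 98.2% (S = 20); 679/690 = 98.4% (S = 23) | 19/30 = 63% | not met |
| Ten leave after one session; 20 attend everything | 410/600 = 68.3% (S = 20); 470/690 = 68.1% (S = 23) | 20/30 = 67% | met |

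Both rows are correct. The second sits on the edge: one absence among the 20 who stay gives 19/30 and fails.

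**Step 2: is the reversal peculiar to this rule?** Count a person as a completer from 90% of sessions, that is 18 of 20. Let 11 people miss three sessions each and nobody leave. Attendance is (600 − 33)/600 = 94.5%, completers are 19/30, and the rule is not met. The second pattern above, at 68.3%, is still met. Someone who misses three of 20 sessions now scores the same as someone who leaves on day one. The reversal comes from scoring each person yes or no; a lower threshold moves it but does not remove it.

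**Step 3: how often would the present rule pass?** P(met) = P(Bin(30, (1 − d)·p) ≥ 20), where d is dropout and p is the chance of a perfect record: a^S if absences are independent, otherwise beta-binomial with the given ICC. Each range covers S = 20 and S = 23.

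| Attendance, dropout | Independent | ICC 0.1 | ICC 0.2 |
|---|---|---|---|
| 95%, none | 0.0001–0.0006 | 0.135–0.205 | 0.573–0.647 |
| 98%, none | 0.409–0.589 | 0.963–0.977 | 0.997–0.998 |
| 98%, 10% | 0.176–0.295 | 0.770–0.816 | 0.927–0.940 |
| 99%, none | 0.968–0.987 | above 0.99 | above 0.99 |

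For an 80% chance of passing with 10% dropout, (1 − d)·p must be 0.718. Those who stay must then attend 98.9% to 99.0% of sessions if absences are independent, 97.9% to 98.1% at ICC 0.1, and 97.1% to 97.2% at ICC 0.2. The answer depends mainly on *a* and the ICC, and the protocol gives neither.

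**Step 4: what would a share-based definition do under heavy dropout?** Take d = 1/3 and *a* = 0.98 among those who stay, with ICC 0 to 0.1. Under the present rule P(met) is 0.005 to 0.10. With completion at 90% of sessions (18 of 20, or 21 of 23) it is 0.405 to 0.563. The demand for a perfect record is what makes a pass unlikely when a third have left.

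**Step 5: does the text on missed sessions contradict the rule?** The statement in Treatment and procedures concerns how much therapy each person must receive. The rule in Outcomes and testing concerns how the group is scored. Requiring no minimum amount from a person is compatible with counting only perfect records towards feasibility.

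**The case for a change.** The strongest argument for the concern is that the reversal in Step 1 needs no attendance model: the group with far better uptake fails and the worse one passes. Low dropout is also a different quantity from few single absences, and nothing in the protocol supports expecting perfect records from two-thirds of people with subacute stroke, depression and aphasia. If absences were independent and attendance 95%, the rule would almost never be met. Scoring by share of sessions would cost one phrase.

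Some of this stands. The counts are right, the rule is demanding, and the rationale runs dropout and absence together. Because it does so, the protocol may have meant completion as staying in treatment. On that reading the first pattern scores 30/30. A definition of completion would settle the matter, but that is missing detail and not an error.

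The rest does not carry. The reversal is shared by the share-based alternative (Step 2). Failure at 95% attendance is wrong only if 95% ought to count as feasible, and the protocol sets no such standard. Absences in groups of three need not be independent either, and a session that falls through may not count as offered. The gain for well-attending groups is bought with easier passes under heavy dropout (Step 4).

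**Conclusion.** The concern does not hold as an error in the plan. The rule is fixed in advance, can be checked from attendance records, and conflicts with no other statement or figure in the protocol. It is strict on the person and lenient on the group, since up to ten of 30 may miss sessions or leave. Its strictness guards against overclaiming feasibility.

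Its practical effect cannot be settled from the documents. At 98% attendance without dropout, P(met) lies anywhere from 0.41 to above 0.99 for ICC 0 to 0.2. These probabilities assume 20 to 23 sessions, 30 people in Group I, and clustering only within persons; the counts in Steps 1 and 2 need only the session number and the group size.

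Experienced statisticians could reasonably prefer a share of sessions, but that loosens the primary criterion and leaves the one-third-dropout pattern passing. An explicit meaning for completion, and attendance reported beside the verdict, would help the reader; the absence of either does not make the rule wrong.

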Intensive Social Interaction for Treatment of Post-Stroke Depression in Subacute Aphasia: The CONNECT Trial

Study Protocol

**[name]^{1, 2, 3 *}; [name]^{4, 5 *}; [name], MSc⁵;
[name], PhD²; [name], PhD⁶; [name]^{2, 7}**

¹ Faculty of Science, Medical School Berlin, Germany

² Department of Neurology, University Medicine Greifswald, Germany

³ Max Planck Institute for Human Cognitive and Brain Sciences, Leipzig, Germany

⁴ Department of Psychology, Freie Universität Berlin, Germany

⁵ Median-Klinik Berlin-Kladow, Germany

⁶ Psychologische Hochschule Berlin, Germany

⁷ German Centre for Neurodegenerative Diseases, Rostock and Greifswald, Germany

* Authors contributed equally.

Correspondence:

[name]. [name]
Medical School Berlin
Naturwissenschaftliche Fakultät
[name]
[name], Germany
E-mail: [contact]

Clinical Trial Registration:

www.clinicaltrials.gov; identifier: NCT04318951.

Last Update:

March 2019

Methods

Study design and setting

Following the CONSORT guidelines, we here present a parallel-group, blinded-assessment, quasi-randomised controlled phase-IIb trial^a in an outpatient rehabilitation centre in Berlin, Germany, between 2020 and 2022 (study acronym: CONNECT). This trial was approved by the ethics review board at University Medicine Greifswald, Germany (file number: BB 033/17). A team of neuropsychologists will obtain written informed consent from all participants, with ample time for questions and reflection to account for aphasia-immanent comprehension problems.

Study sample and power analysis

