As a *co-primary* outcome of potential efficacy, we will administer a 20-item version of the BDI.³⁴ This self-report measure is known for its excellent psychometric properties, including construct validity and test-retest reliability, in individuals *without* aphasia. The BDI has been successfully piloted in individuals *with* aphasia, as indicated by phase-IIA RCT data.²⁰ To complement the BDI, we will use a clinician-rated measure with good psychometric properties as an additional *co-primary* outcome, a 7-item version of the Hamilton Rating Scale for Depression.³⁵

Reflecting the potential influence of treatment-induced or spontaneous progress in verbal expression on change in depression severity, we will employ the combined Aachen Aphasia Test (AAT) subscales “Repetition” and “Naming” as a *secondary* outcome and covariate in our analyses.³⁶ These two AAT subscales proved to be most sensitive to ILAT-mediated gains in chronic aphasia, as shown by RCT data.^{19, 23} Moreover, participants will complete the Self-Efficacy Questionnaire, a self-report measure conceived to quantify personal confidence in overcoming obstacles when accomplishing difficult tasks.³⁷ Low scores on this *secondary*

outcome constitute a risk factor for cognitive-affective distress, suggesting a significant negative relationship between results on the Self-Efficacy Questionnaire and BDI.³⁸ The Self-Efficacy Questionnaire will provide an external criterion to determine the psychometric adequacy of our self-report co-primary outcome, the BDI, in individuals with aphasia, given the possibility of serious deficits in understanding spoken instructions not ruled out during eligibility screening, as specified above.

A neuropsychologist blinded to group allocation will conduct all diagnostic sessions. The neuropsychologist will have substantial experience in communication with individuals suffering from aphasia-immanent comprehension problems. Testing will take place immediately before (baseline: T₁; BDI, HAM-D, and AAT) and within 24 hours after the 1-month treatment period (endpoint: T₂; BDI, HAM-D, AAT, and Self-Efficacy Questionnaire).

References

- 1 Lewinsohn PM. A behavioral approach to depression. Friedman RJ, Katz MM, editors. In: *Psychology of Depression: Contemporary Theory and Research*. Wiley; 1974. p. 157–178.

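### The timepoint of the AAT covariate is not stated; a T2 or change score would stop the BDI and HAM-D comparisons from estimating ILAT's total effect on depression

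*Combined protocol and SAP*

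**What the plan says.** All of the relevant text is in the combined protocol and SAP.

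- **Role of AAT (Outcomes and testing).** The combined Repetition and Naming subscales are a secondary "outcome and covariate in our analyses". The reason given is: "Reflecting the potential influence of treatment-induced or spontaneous progress in verbal expression on change in depression severity".
- **Why these subscales (same section).** "These two AAT subscales proved to be most sensitive to ILAT-mediated gains in chronic aphasia".
- **When AAT is measured (same section).** At both visits: "Testing will take place immediately before (baseline: T₁; BDI, HAM-D, and AAT" and "endpoint: T₂; BDI, HAM-D, AAT, and Self-Efficacy Questionnaire".
- **What the comparison is for.** The title is "Intensive Social Interaction for Treatment of Post-Stroke Depression in Subacute Aphasia", and the BDI is introduced as a co-primary "outcome of potential efficacy, we will administer a 20-item version of the BDI". The HAM-D is a further co-primary outcome.
- **Power analysis (Study sample and power analysis).** It gives "number of covariates: 2" and names neither. The same section says the trial should sharpen the effect-size estimate for a phase-III trial.

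No model is written for the BDI or HAM-D, no estimand is stated, and nothing says whether the AAT covariate is the T1 score, the T2 score or the change.

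**The concern.** Two readings are open. The covariate may be T1 AAT, since the sentence giving the reason also introduces AAT as a secondary outcome and may refer mainly to that role. Or it may be T2 AAT or AAT change, since only those can reflect progress made during the trial, which is the reason stated.

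Under the second reading the model conditions on something treatment may have changed. The protocol gives grounds to expect this: it picked these subscales for their sensitivity to ILAT (in chronic aphasia, so not established for this subacute sample), and Treatment and procedures sets ILAT at five one-hour sessions a week against 2–3 hours of speech-language therapy in standard care. If ILAT improves language and language relates to mood, part of the ILAT effect is adjusted away. What remains is a clean direct effect only if language recovery and mood share no unadjusted causes. General recovery after stroke is an obvious candidate for such a cause.

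At stake are both co-primary efficacy estimates and the effect size handed to phase III. With the choice left open, it could also be made after the data are seen.

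**Working it through.** **1. The plan's own figures reproduce.** Inputs from Study sample and power analysis: η² = 0.132, α = 0.05, power 0.80, two groups, numerator df 1, two covariates, 10% dropout.

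- f = √(0.132 / 0.868) = 0.390.
- Noncentral F with noncentrality N × f². At N = 54: 54 × 0.390² = 8.21, and power with df 1 and 50 is 80.2%.
- 54 / 0.9 = 60.

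**2. The covariate count does not reveal the covariates.**

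| Covariates | 0 | 1 | 2 | 3 |
|---|---|---|---|---|
| Power at N = 53 | 79.5% | 79.5% | 79.5% | 79.4% |
| Power at N = 54 | 80.3% | 80.3% | 80.2% | 80.2% |

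N = 54 is the answer in every case.

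**3. What adjusting for AAT change would do.** Assumptions, none of them in the documents:

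- The total effect is d = 2f = 0.78. The protocol does not say whether the η² it used was a total effect.
- Within-arm variances are 1.
- gain = between-arm difference in AAT change, in SD units.
- r = within-arm correlation of AAT change with improvement in depression.

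Adjusted effect = 0.78 − r × gain. Noncentrality at N = 54 = (54/4) × effect² / [(1 − r²)(1 + gain²/4)], df 1 and 50. For example, gain 0.5 and r 0.3: 0.78 − 0.15 = 0.63, and 13.5 × 0.63² / (0.91 × 1.0625) = 5.54, which gives 63.6% power.

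The last column is the total two-arm N that a phase-III planner would derive from the effect (80% power, no covariates).

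| Gain | r | Adjusted effect | Shift | Power at N = 54 | Phase-III N |
|---|---|---|---|---|---|
| 0 | any | 0.78 | 0 | 81.8–90.1% for absolute r of 0.2–0.5 | 54 |
| 0.1 | 0.2 | 0.76 | −3% | 79.7% | – |
| 0.3 | 0.2 | 0.72 | −8% | 74.5% | 64 |
| 0.3 | −0.2 | 0.84 | +8% | 86.3% | 48 |
| 0.5 | 0.3 | 0.63 | −19% | 63.6% | 82 |
| 0.5 | −0.3 | 0.93 | +19% | 92.6% | 40 |

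**4. T1, T2 or change.** In a large simulation with gain 0.5, a language-to-mood path of 0.3 and a true total effect of 0.78, the group coefficient was 0.78 with T1 AAT, 0.68 with T2 AAT and 0.63 with AAT change. With no ILAT effect on AAT, all three gave about 0.78.

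**5. The adjusted figure need not be a direct effect.** In 20,000 simulated trials of 27 v 27, r was produced either by a causal path from language to mood or only by a shared cause, in which case the true direct effect is 0.78.

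| Gain, r | Causal path: estimate (true direct) | Shared cause only: estimate (true direct) |
|---|---|---|
| 0.3, 0.2 | 0.722 (0.72) | 0.718 (0.78) |
| 0.5, 0.3 | 0.628 (0.63) | 0.631 (0.78) |

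The estimates are nearly the same in both situations, so the data alone cannot separate them. Without AAT change in the model, the mean estimate was 0.777–0.784 in every setting.

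**The case against.** **The harm is conditional.** The protocol never says that T2 or change will be used. A shift also needs ILAT to move AAT between arms, and AAT change to correlate with mood. All of this stands, and it is why the conclusion is put conditionally. But the stated reason for adjusting points to the reading that causes the problem.

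**A language-independent effect may be what is wanted.** The title stresses social interaction, and Treatment and procedures gives positive reinforcement as the route to better mood. The question could be whether ILAT helps beyond any language gain. That is a legitimate question, but it is a different estimand, and it would have to be stated with its assumption about shared causes.

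**T1 adjustment does not guarantee the right answer here.** Allocation depends on whether enough fellow players are available, so recovery may be unbalanced between arms. Suppose r = 0.2 arises only from a shared recovery cause (loading √0.2 = 0.447 on both AAT change and mood), gain is 0.3, and the ILAT arm is ahead by 0.3 SD on that cause. Without AAT change the estimate is 0.78 + 0.447 × 0.3 = 0.91; with it, 0.914 − 0.2 × (0.3 + 0.134) = 0.83, nearer the true 0.78. The limitation is real. If the control arm is ahead by 0.3 SD instead, the figures are 0.78 − 0.134 = 0.65 and 0.646 − 0.2 × (0.3 − 0.134) = 0.61, so adjusting moves the estimate further from the truth. Post-treatment adjustment is therefore no dependable repair for the allocation.

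**The shifts are small beside sampling error.** At N = 54 and d = 0.78, the approximate 95% interval is 0.23 to 1.33. That is true, but imprecision shrinks when data are pooled or the trial is enlarged, and estimating a different quantity does not. The phase-III numbers are also slightly sensitive to method: carrying the reduced residual variance and two covariates into the calculation turns 82 into 79 and 64 into 62.

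**Conclusion.** The point holds. The timepoint of the AAT covariate is open, and the protocol's own reason for adjusting points to a post-baseline score. If such a score is used, the BDI and HAM-D comparisons do not estimate the total effect, which is what the title and the efficacy label suggest. They estimate a direct effect only under an unstated no-shared-causes assumption.

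The size cannot be taken from the documents. In the cases tabulated for AAT change it runs from −19% through zero to +19% of an assumed 0.78. The effect is understated if ILAT improves AAT and better AAT goes with lower depression, overstated if that correlation has the opposite sign, and unchanged in expectation if the arms do not differ in AAT gain. The sample size is correct and the feasibility outcome is untouched. This should be fixed before analysis; confidence is moderate because the text also permits T1.

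**What to change.** State in Outcomes and testing, or in a short analysis section, that T2 BDI and, separately, T2 HAM-D are regressed on group with two pre-treatment covariates: the T1 score of the same measure and the T1 AAT composite. Name the same two in the power analysis. Keep T2 AAT as a secondary outcome. Put any adjustment for T2 AAT or AAT change in a labelled exploratory analysis that states the no-shared-causes assumption and is not used for the efficacy conclusion or phase-III planning. If a language-independent effect is intended, say so as a separate estimand.

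The cost is wording only: all three T1 measures are already collected, the covariate count stays at two, and N stays at 54 (60 with dropout). The downside is that the main model will not adjust for differences between arms in spontaneous language recovery during treatment, which allocation by availability of fellow players may not balance. The exploratory analysis can examine these, subject to its assumption.
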